3.3.3.1 Description of the Missing Data

To examine the nature of missing data, cohorts of subjects will be defined based on the scheduled assessments that were completed.

For each of the primary endpoints there will be 3 cohorts of based on the FAS (based on the post-baseline data included in the primary analysis):

1. Subjects who have a Week 35 assessment only
2. Subjects who have a Week 66 assessment only
3. Subjects who have Weeks 35 and 66 assessments

For each endpoint plots will be produced, illustrating the mean change from baseline over time in each of the cohorts. These will be based on the observed data for each of the cohorts. The trends over time will be visually compared across cohorts to explore patterns of missing data. Of particular interest is the group that has complete follow-up data available (i.e. have Weeks 35 and 66 assessments) and the group with a Week 35 assessment only. This can help indicate if subjects show any sign of decline in their efficacy prior to dropping out from the study.

3.3.3.2 Multiple Imputation Methodology

For each of the primary endpoints, sensitivity analyses will be performed in the Safety Set using multiple imputation methods based on pattern mixture models. First, a repeated measures Gaussian model will be fitted to the data using a Bayesian approach, with non-informative priors for the mean and variance-covariance matrix to provide a joint posterior for the parameters in this model. The repeated measures Gaussian model will include separate mean profiles for each treatment group and the same covariates as those in the primary MMRM analysis.

Independent samples will then be drawn from the posterior distributions for the mean and variance-covariance matrix to provide inputs into an imputation model. For each subject with missing data, these sampled values of the parameters for mean vectors and the variance-covariance matrices specify a joint distribution for their observed and unobserved outcome data.

The post-withdrawal part of each pattern-specific distribution will be modelled using three different approaches discussed below. This imputation model will have the same covariates as those in the primary MMRM analysis.

Based on this imputation model, a single set of data will be sampled for the missing data based on the distribution for the subject's missing data conditional upon their observed data.

The post-withdrawal part of each pattern-specific distribution will be modelled using these three approaches:

1. Missing at Random (MAR) approach.

The means and variance-covariances following withdrawal are chosen to reflect the subject's own treatment group. This approach should provide similar numerical results to the primary analysis.

2. Copy Increment from Reference (CIR) approach.

The CIR approach is detailed in Carpenter et al. (2013) and addresses a potential pattern of informative missingness where the assumption is that the active Study Drug halts or slow

disease progression, and the disease progresses after treatment is discontinued. In CIR missing data in the placebo group will be imputed under a within treatment arm MAR assumption. For a patient in the active treatment group their mean profile (i.e. mean increments) will track that of the placebo group, but starting from the benefit obtained.

3. Jump to reference (J2R) approach.

The J2R approach is detailed in Carpenter et al. (2013) and is an extremely conservative imputation approach that assumes that a patient receiving active Study Drug does not sustain benefit after discontinuing study treatment. In J2R missing data in the placebo group will be imputed under a within treatment arm MAR assumption. For a patient with missing data in the active treatment group their mean response distribution is set to equal that of the placebo group.

For each imputation method used, at least 5000 imputed datasets will be generated. The imputed observations in each dataset will be checked to ensure they are within the possible change from baseline range for the particular subject they belong to. If a dataset contains out-of-range values, it will be discarded and a new dataset will be generated until there are 5000 datasets which contain no out-of-range values. Each of 5000 imputed data set will then be analyzed using simple analysis of covariance (ANCOVA) model at Week 66 and the resulting treatment differences and their standard errors will be combined using Rubin's rules. The ANCOVA model will include fixed effects for treatment (two levels), and each of the 3 randomization stratification factors (each with two levels) with baseline value of the endpoint as the covariate. Note that in these analyses efficacy assessment that are within the analysis window but more than 52 days after last dose will be included. This is different from the primary analysis, where data after 52 days from last dose is excluded. The number of imputed datasets may be increased after review of results if the simulation error is considered large.

A random seed to be used by a random number generator with value of 2855 will be used to initiate data imputation for all three methods.

3.3.3.3 Sensitivity Analysis Using Data at Withdrawal Visit

The primary outcome variable, modified Neuropathy Impairment Score +7 (mNIS+7) score, is measured on treatment at baseline, Week 35 and Week 66. The primary analysis is the difference between the active treatment and placebo at week 66 based on a repeated measures model for Week 35 and Week 66 data using treatment-by-time 2*2 factorial, baseline-by-time and strata covariate fixed effects, and an unstructured 2*2 covariance matrix shared across treatments. The analyzed response is difference from baseline in mNIS+7, but the treatment difference will be the same as if the absolute value of mNIS+7 were analyzed instead, since baseline-by-time covariate is included in the model.

In order to include the values of mNIS+7 at withdrawal visit in the analysis the following model is fitted as a sensitivity analysis in the Safety Set. Care needs to be taken with its interpretation as these withdrawal visit measurements may be extreme. The absolute value of mNIS+7, and not change from baseline, will be used as response. This is done for simplicity of expression of the

model and makes no difference to the results. The following model is equivalent to the previous primary analysis model when there are no withdrawal visit data. The only difference will come from the inclusion of the additional data from exit visits. If strata had been crossed with time or strata excluded from the primary analysis then they would be algebraically identical. The model is simply a re-expression of the primary analysis model that allows one to include data measured at times other than Weeks 35 and 66.

To implement this model, 3 time parameters should be defined as follows:

CCI

CCI

CCI

The other primary endpoint, Norfolk QOL-DN, will also be analyzed using the methods described in this section.

3.3.4 Subgroup Analyses of Primary Endpoints

Subgroup analyses will be conducted for each of the two primary efficacy endpoints in the FAS. Subgroups defined by the following variables will be evaluated:

- V30M TTR mutation (Yes, No)
- Age (< 65 years old, ≥ 65 years old)
- Race (White, non-White)
- Sex (Male, Female)
- Region (North America, Europe, South America/Australasia)
- Previous treatment with Vyndaqel® or Diflunisal (Yes, No)
- Disease stage (Stage 1, Stage 2)
- CM-ECHO Set (Included, Not included)

The MMRM for the change from baseline will include fixed categorical effects for treatment (two levels), time (two levels), each of the 3 randomization stratification factors (each with two levels), treatment-by-time interaction, treatment-by-subgroup interaction, and treatment-by-time-by-subgroup interaction. The baseline value of the endpoint and the baseline-by-time interaction will be included as covariates in the model. The treatment-by-subgroup interaction at each timepoint will be tested at the significance level of 0.10. Treatment group differences will be evaluated within each category of the subgroup, regardless of whether the interaction is statistically significant.

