2.2 Randomization & Treatment Allocation

Almac Clinical Technologies is responsible for providing the randomization for this study. Patients will be randomized after all screening assessments have been completed and after the Investigator has verified that they are eligible. No patient may begin treatment prior to randomization and assignment of a unique subject identification number.

Using an Interactive Voice-Response System (IVRS), eligible patients will be randomized 2:1 to receive ISIS 420915 or placebo, respectively. There will be 2 separate and independent randomizations, one for patients in the PK subgroup (approximately 20) and one for patients who are not in the PK subgroup (approximately 115). Within each subgroup, randomization will use a permuted block schedule using the 8 combinations of the following 3 binary stratification variables:

- Previous treatment with Vyndaqel® or Diflunisal versus no known previous treatment
- Stage 1 versus Stage 2 disease
- V30M TTR mutation versus non-V30M TTR mutation

A description of the randomization process, including block size and the procedure to follow will be provided in a separate document prepared by Almac Clinical Technologies.

The randomization list will be generated prior to enrollment of any patients. The Sponsor Quality Assurance department or designee will hold a copy of the randomization lists generated by the IVRS vendor.

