3.2.1 Analysis Conventions

All reporting will be performed in SAS version 9.1.3 or higher.

Efficacy results will be summarized under the treatment to which patients were randomized. Safety and PK results will be summarized under the treatment which patients actually received. Should there be any cases after unblinding in which a patient received treatment other than what was randomized, such cases will be discussed in the study report and noted in footnotes where applicable.

All electronic case report form (eCRF) data, lab data transfers, echocardiogram, ECG, and mNIS+7 score data, as well as any outcomes derived from the data, will be provided in the patient data listings. Patient data listings will be presented for all patients enrolled into the study, and will be sorted by treatment group, subject ID, visit, and time point (where appropriate).

Central laboratory assessments will be included in the summary tables, local laboratory assessments will only be included in listings. Exceptions to the use of local laboratory assessment in summary tables is made for platelets, where summary tables will use both local and central laboratory results

All tables will present the population frequencies in each treatment group and/or subgroup (where appropriate) and will indicate the number of subjects with non-missing data and the denominators for percentages.

Descriptive summary statistics including n, mean, percentiles (e.g., median, P25, P75), standard deviation, and range (minimum, maximum) for continuous variables, and counts and percentages for categorical variables, will be used to summarize data by treatment group. Summaries of pharmacokinetic parameters will also present geometric mean, standard deviation of log-transformed data, and CV%. Where appropriate, p-values will be reported. All statistical tests will be conducted using 2-sided tests with a 5% Type I error rate unless otherwise stated.

[figure not shown]
Age will be presented in years. Weight will be presented in kg. Height will be presented in cm. Temperature will be presented in °C. Laboratory values will be summarized using standard units.

Precision for displays will use the following conventions. Means, percentiles (e.g., median, P25, and P75), least squares means, difference in least squares means will be displayed to one more decimal place than measured values. Standard deviations and standard errors will be displayed to two more

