The planned sample size for this study was revised from 195 to 135 using information published from the placebo controlled Phase 3 Diflunisal trial (Berk et al. 2013), a retrospective, multinational natural history study in 283 FAP patients (Adams et al. 2015), and uncontrolled data using another TTR mRNA targeted therapeutic (Adams 2015). It is estimated that the placebo group will have a 16 point increase in the mNIS+7 score from baseline to Month 15, and the treated group will have a 6.4 point increase in mNIS+7. The standard deviation of the change from baseline in each treatment group is estimated to be 14. With 135 patients (2:1 allocation ratio) there would be at least 90% power to detect a 9.6 point difference in the change from baseline in the mNIS+7 score between the 2 groups, with a two-sided t-test of 5% alpha, assuming that the dropout rate is approximately 25%. For the Norfolk QOL-DN questionnaire total score, it is estimated that the placebo group will have a 13.3 point change from baseline to Month 15, the treated group will have a 2.6 point change from baseline and the standard deviation of the change from baseline in each treatment group will be 18. With 135 patients, there would be at least 80% power to detect a 10.7 point difference in the change from baseline in the Norfolk QOL total score between the 2 groups, with a two-sided 5% alpha level, assuming that the dropout rate is approximately 25%.

5 Interim Analyses

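### Does leaving the subgroup main effect and time-by-subgroup out of the SAP 3.3.4 model spoil the interaction tests?

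*SAP*

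**What the plan says.** SAP 3.3.4 defines eight subgroup variables. Seven have two levels and one has three: "Region (North America, Europe, South America/Australasia". The model sentence begins "The MMRM for the change from baseline will include fixed categorical effects for treatment (two levels), time (two levels), each of the 3 randomization stratification" and ends with "treatment-by-time interaction, treatment-by-subgroup interaction, and treatment-by-time-by-subgroup interaction". Baseline and baseline-by-time are added as covariates.

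The section then states the test: "The treatment-by-subgroup interaction at each timepoint will be tested at the significance level of 0.10". It also states what is reported whatever that test shows: "Treatment group differences will be evaluated within each category of the subgroup, regardless of whether the interaction is statistically significant".

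Three of the eight variables (V30M mutation, previous treatment, disease stage) are also the randomization factors. SAP 2.2 describes the blocks as formed "using the 8 combinations of the following 3 binary stratification variables". Their main effects are therefore already in the model. SAP 3.2.1 adds "All reporting will be performed in SAS version 9.1.3 or higher".

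**The concern.** A model with an interaction normally carries the lower-order terms as well. Here age, race, sex, region and CM-ECHO Set enter only through their products with treatment, and none of the eight variables has its own time course. The same SAP keeps the usual order in Sensitivity Analysis 9, where pooled site is added as a main effect before its interaction with treatment is examined.

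When SAS builds a categorical treatment-by-subgroup term without the subgroup main effect, that term absorbs the main effect. The output row is still labelled treatment-by-subgroup, but for those five variables it tests prognosis and interaction together. Section 3.3.4 sets a formal 0.10 level without writing out a contrast or its degrees of freedom. If that row were reported, a factor that speeds progression equally in both arms could be described as modifying the treatment effect on either primary endpoint.

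**Working it through.** **Inputs.** From SAP 4: 135 patients, 2:1 allocation, about 25% dropout, and for mNIS+7 "The standard deviation of the change from baseline in each treatment group is estimated to be 14". Evaluable: 135 × 0.75 = 101.25, taken as 101, split 67 and 34. From SAP 3.3.4: interaction level 0.10. The SAP gives no subgroup splits, no prognostic gaps, no correlation between visits and no Week 35 SD. Values for these below are assumptions.

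**The plan's own figures.** The only figure for these tests is the 0.10 level. As a check on the inputs, a two-sided 5% t-test with 67 and 34 patients gives power 0.897 for 9.6 points with SD 14, and 0.798 for 10.7 points with SD 18. The normal approximation gives 0.902 and 0.805. The stated 90% and 80% are reproduced.

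**Step 1: what the listed terms span.** With categorical coding, rank of the treatment × time × subgroup part of the design:

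| Terms entered in order | Two-level, not a stratum | Region | Stratification factor |
|---|---|---|---|
| Intercept, treatment, time, treatment-by-time | 4 | 4 | 4 |
| + subgroup main effect | not listed | not listed | 5 |
| + treatment-by-subgroup | 6 (adds 2) | 8 (adds 4) | 6 (adds 1) |
| + treatment-by-time-by-subgroup | 8 (adds 2) | 12 (adds 4) | 8 (adds 2) |
| Number of cells | 2×2×2 = 8 | 2×2×3 = 12 | 2×2×2 = 8 |

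In every column the listed terms reach the full factorial. With the stratification and baseline terms included, the listed model, the full-factorial model and the two combined have equal rank: 13, 13, 13 for a two-level non-stratum variable; 17, 17, 17 for region; 12, 12, 12 for a stratification factor. They are the same fitted model.

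**Step 2: the test at each visit.** At visit v, for a two-level subgroup, the interaction is

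(active − placebo in level 2) − (active − placebo in level 1).

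This is a contrast of cell means. All cell means are free in the listed model, so the contrast is estimable and identical in both models: 1 df, or 2 df for region. A prognostic shift common to both arms cancels. In the Wald calculation its size is 0.10 for every shift tried, 0 to 10 points. In simulation (4,000 trials per case, 50:50 and 80:20 splits) it ran from 0.095 to 0.106.

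**Step 3: the row that would mislead.** The treatment-by-subgroup row has 2 df for age, race, sex and CM-ECHO Set, and 4 df for region. It averages over Weeks 35 and 66. Assume a 50:50 split, SD 14 at both visits, correlation 0.6, a Week 35 gap half the Week 66 gap, and no true interaction:

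- average gap = (1 + 0.5)/2 × gap = 0.75 × gap
- variance of a patient's two-visit average = 196 × (1 + 0.6)/2 = 156.8
- noncentrality = 101 × 0.5 × 0.5 × (0.75 × gap)² / 156.8 = 0.0906 × gap²

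| Gap at Week 66 | Noncentrality | Rejection, F(2, 93) at nominal 10% |
|---|---|---|
| 3 points | 0.82 | 19% |
| 5 points | 2.26 | 36% |
| 8 points | 5.80 | 68% |

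With a Week 35 SD of 10 the rates are 21%, 41% and 76%; for region, 18%, 34% and 68%. A 2-df test at Week 66 alone would give 23%, 46% and 82%, but the listed model prints no such row.

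**Step 4: the three stratification factors.** Their treatment-by-subgroup row keeps 1 df and has size 0.10. It is a valid interaction test averaged over visits. The three-way row does pick up prognosis that changes between visits, for all eight variables (24% at a 5-point gap), but 3.3.4 does not name it as the test.

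**The case for a change.** The strongest case for an edit is that a prespecified test should not depend on which line of output is read. The hypothesis and the misleading row share a name, no contrast is written, and a sentence or two would settle it. The inflation under the wrong reading is real, and the degrees-of-freedom result behind it needs no assumptions. If the terms were coded as numeric 0/1 products, the omission would bias the estimate itself: with a true interaction of zero and a 5-point prognostic shift, the product coefficient came out near 5.

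What stands is that the listing is incomplete and the contrast is left to the programmer. The rest does not carry. The section specifies categorical effects, which rules out the product coding. It asks for a result at each timepoint, and one row averaged over two visits cannot supply that. An analyst following the text has to construct visit-specific contrasts, and these are correct. Writing in the extra terms would change the labels and degrees of freedom of rows the plan does not use, and no planned estimate or p-value.

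**Conclusion.** The omission is real but does not affect any planned result. Under the categorical coding the SAP states, the fitted model, the within-subgroup differences and the Week 35 and Week 66 interaction contrasts are the same as in the fully listed model, and the contrasts hold their 10% level. This rests on rank arithmetic, not on assumed data.

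What remains is missing detail that a competent programmer fills in the intended way. The risk is confined to misreading one row for five of the eight variables. Its size (about 19%, 36% and 68% for gaps of 3, 5 and 8 points) depends on an assumed 50:50 split, correlation, Week 35 gap and SD, none of which the documents give. The subgroup analyses are supportive, the within-category differences are reported in any case, and the primary inference on both endpoints is unaffected. No change to the plan follows.

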3.4 Secondary Analyses

Secondary analyses include the analysis of secondary endpoints and pharmacodynamic analyses.

3.4.1 Secondary Efficacy Endpoint Definitions

Secondary efficacy endpoints are:

- Change from baseline to Week 66 in the Norfolk QOL-DN questionnaire symptoms domain score (Stage 1 patients only) and the Norfolk QOL-DN questionnaire physical functioning/large fiber neuropathy domain score (Stage 2 patients only)
- Change from baseline to Week 65 in the Modified Body Mass Index (mBMI)
- Change from baseline to Week 65 in the Body Mass Index (BMI)
- Change from baseline to Week 66 in the NIS
- Change from baseline to Week 66 in the modified +7

- Change from baseline to Week 66 in the NIS+7
- Change in GLS by ECHO from baseline to Week 65 in the Randomized Set, ECHO subgroup and in the CM-ECHO Set

Treatment group differences will be evaluated using the same method as the primary efficacy analysis (MMRM described in Section 3.3.2). These analyses will be conducted on both the FAS and the PPS populations. The analysis for GLS will be specified in the ECHO SAP.

The normality assumptions for the MMRM will be assessed for each of the secondary endpoints by inspecting the following plots:

- Histogram of marginal studentized residuals derived from the MMRM model.
- Normal probability plot.

The non-parametric Van-Elteren test may be performed as a sensitivity analysis, if deemed necessary. Hodges-Lehmann estimates of the differences between ISIS 420915 300 mg group and the placebo group as well as distribution-free confidence intervals based on the Wilcoxon Rank Sum Test will also be provided.

3.4.2 Pharmacodynamic Endpoint Definitions

Pharmacodynamic endpoints are:

- Change and percent change from baseline to Week 65 in TTR level
- Change and percent change from baseline to Week 65 in RBP4 level.

Analyses of the pharmacodynamic endpoints will be evaluated using the same method as the primary efficacy analysis (MMRM described in Section 3.3.2). All pharmacodynamic analyses will be conducted on both the FAS and the PPS.

In addition the proportion of subjects with percentage decrease from baseline in plasma transthyretin (TTR) $\geq 60\%$ will be summarized by treatment group at each visit.

3.5 Tertiary Analyses

The tertiary efficacy analyses will assess whether ISIS 420915 is superior to placebo as measured by the following endpoints:

- Change from baseline to Week 65 in the SF-36 in the Physical Component Summary score, the Mental Component Summary score, and mental health domain score.
- Change from baseline to Week 66 in the individual components of the NIS score (cranial nerves, muscle weakness, reflexes, and sensory)
- Change from baseline to Week 66 in individual components of the modified +7 score (heart rate to deep breathing, nerve conduction, heat-pain sensory, and touch-pressure sensory)

- Change from baseline to Week 66 in individual components of the +7 score (heart rate to deep breathing, nerve conduction and vibration detection threshold)
- Change from baseline to Week 66 in the +7 score
- Change from baseline to Week 66 in individual domain scores of the Norfolk QOL-DN (physical functioning/large fiber neuropathy, symptoms, activities of daily living, small fiber neuropathy, and autonomic neuropathy)

Analyses of the tertiary endpoints will utilize the MMRM described in Section 3.3.2. All tertiary analyses will be conducted on the FAS (Note that the study protocol specified these endpoints would additionally be assessed in the PPS).

Similar to the primary endpoints, by-visit descriptive statistics will be provided for the individual mNIS+7 components, Norfolk QOL-DN questionnaire domain scores, PD assessments, and SF-36 domain scores. At the end of study, the summaries will be updated to include the Post-Treatment follow-up visits if supported by adequate data.

